6.5 General Considerations for Statistical Analysis

All statistical tests will be two-sided and a difference resulting in a p-value of less than or equal to 0.05 will be considered statistically significant. All p-values will be rounded to and displayed in four decimals. If a p-value less than 0.0001 occurs it will be shown in tables as <0.0001.

There will be no multiplicity adjustments, or adjustments for multiple comparisons.

Descriptive summaries of variables will be provided where appropriate. For continuous variables, the number of non-missing values (n) and the median, mean, standard deviation, minimum, and maximum will be tabulated by treatment. For categorical variables, the counts and proportions of each value will be tabulated by treatment. Expansion of descriptive table categories within each treatment may occur if such elaborations are thought to be useful.

All collected data will be presented in listings. Data not subject to analysis according to this plan will not appear in any tables or graphs but will be included in the data listings.

Post-hoc exploratory analyses not identified in this SAP may be performed to further examine the study data. These analyses will be clearly identified as such in the final clinical study report. The SAP will not be amended for post-hoc, additional analyses identified after planned analyses are completed. Likewise, the list of planned tables (Section 8.1) is the list of planned tables prospectively defined for the study analyses. Additional tables and figures may be defined to further evaluate study results and the SAP will not be amended to list these additional analysis tables.

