6.7.4 Statistical Modeling: Graphic Displays of Study Results

Graphical displays of study endpoints will be completed and include both observed study data and modeled analyses. Arithmetic means, Least Square Means (LS Means), LS means differences, and appropriate measure of dispersion (e.g. standard deviation, standard error) or confidence intervals may be display in figures to augment the modeled analysis. In general,

graphical displays will be accompany each planned analysis to present study results, utilizing companion numbering aligned with tabular numbering.

Scatter points over the observation time intervals for UX001-CL201 through the 6-month (24 week) time point for UX001-CL202 will be completed for each study endpoint, by treatment pathway (Table 3), to examine trends in results over time of treatments for subjects who roll-over from UX001-CL201. Treatment Naïve subjects enrolled in Part II of UX001-CL202 will have the scatter plots scaled for their participation with treatment 12g/day SA-ER/SA-IR. In general the scatterplots will include, for any given endpoint, all observations for every subject presented in a single figure, color coded for treatment pathways.

Bar charts will be completed for each endpoint where change from baseline is examined and treatment differences are evaluated. Either the mean change or LS Mean's differences, whichever is appropriate for the endpoint, will be displayed to support the statistical analyses performed.

Exploratory scatter plots, and correlations, will be completed to examine study endpoint means (or LS means) compared to Free Sialic Acid (SA), and other serum biomarkers of interest, to explore the treatment effects with the 12g/day SA-ER/SA-IR dose compared to previous doses subjects (Table 3).

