A GEE model (see Section 6.7.2) will be completed for the week 24 (6 month) primary analysis will include the visits from in Part II of UX001-CL202 (Months 1 to 6) accounting for time on the 12g/day SA-ER/SA-IR treatment with subjects who cross-over from treatment administered in UX001-CL201 (Table 3). The GEE model will incorporate the treatment groups defined in the planned comparisons (Table 8) for HHD % predicted normal strength scores.

Additional Analyses: HHD UE, LE Scores

In addition to the above analyses, additional analyses will be conducted to help further assess both the degree of change over the time course of treatment in both UX001-CL201 and in UX001-CL202 and the effect of crossover from the dosing pathways (Table 3). For each of the treatment pathway groups (or combinations thereof) the HHD UE and LE composite change over time will be evaluated to seek understanding on the various dosing pathways and the effect of the 12g/day SA-ER/SA-IR dosing.

The cross-over treatment pathway groups may be compared with the change observed in prior treatment period HHD UE and LE scores. Trends in the change observed in each parameter will be displayed using graphical techniques. These latter analyses will help evaluate an effect of SA over an extended period of time from UX001-CL201 through UX001-CL202, as well as on the reversal of HHD change for subjects that may have declined during the placebo period (Weeks 0-24 in UX001-CL201). These analyses will help to understand the long term impact of treatment over dosing pathways and assess whether the rate of change in individual subjects has changed significantly from before to after the various treatments received.

Additional Analyses: Serum SA Levels and HHD UE, LE Scores

An analysis of change in mean serum SA level impact on HHD UE, LE scores will be performed. Changes in mean serum SA level observed during the cross-over treatment pathway groups may be compared with the change observed in prior treatment period HHD UE and LE scores. Trends in these changes in observed SA levels and HHD UE and LE scores will be displayed using graphical techniques.

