Subjects achieving a mean change in serum SA of 0.1 mg/dl or greater over their individual baseline over all visits may be compared to those subjects with <0.1 mg/dl mean change in SA level. Subjects will be placed into either the 0.1 mg/dl or greater mean difference group or the less than 0.1 mg/dl mean difference group, and then the change in HHD UE and LE scores will be compared across these two groups using a GEE model.

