6.9 Statistical Analysis: Pharmacokinetics

6.9.1 Free Serum Sialic Acid (SA) Levels

Blood samples for the measurement of trough levels of free serum SA will be drawn during blood draws for clinical laboratory samples. Free serum SA samples are being assessed at baseline and the Part I termination visit, and at months 1, 3, 6, 12, 24, 36, and the termination visit in Part II in UX001-CL202 for subjects who roll-over from UX001-CL201. Treatment Naïve subjects who are enrolled in Part II of this study will have a baseline assessed at the screening visit.

Free SA levels in serum assess the drug concentration in the bloodstream resulting from treatment and are the best indicator of compliance with the treatment regimen. Free SA levels in serum are expressed in micrograms of SA per ml of serum. Free serum SA levels observed for the 12g/day SA-ER/SA-IR dose will be evaluated at each study time point using descriptive statistics.

The change in free serum SA level from Baseline to the 6-month Part II time point will be analysed using a GEE model with baseline free serum SA level as a covariate for the 12g/day SA-ER-SA-IR dose group in Part II. Comparisons identified in [Table 8](#) will be implemented for this analysis.

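### The only specified model linking serum sialic acid to HHD strength splits a continuous exposure at an unexplained 0.1 mg/dl, a different unit from the one in which SA is expressed

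*SAP*

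**What the plan says.** The block on serum SA and HHD in SAP 6.7.6 has three parts.

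- A commitment: "An analysis of change in mean serum SA level impact on HHD UE, LE scores will be performed". No method is named for it.
- A display: "Trends in these changes in observed SA levels and HHD UE and LE scores will be displayed using graphical techniques".
- An optional split: "Subjects achieving a mean change in serum SA of 0.1 mg/dl or greater over their individual baseline over all visits may be compared" with those whose mean change is below the cut. The rule is stated as: "Subjects will be placed into either the 0.1 mg/dl or greater mean difference group or the less than 0.1 mg/dl mean difference group". Once subjects are classified, "the change in HHD UE and LE scores will be compared across these two groups using a GEE model".

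The cut of 0.1 mg/dl has no stated basis. The individual baseline is not tied to any one of the several listed in SAP 6.5.8.

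On units, SAP 6.9.1 states: "Free SA levels in serum are expressed in micrograms of SA per ml of serum". Table 5 (SAP 5.3) says only that laboratory units are standardized across the study. Table 7 (SAP 5.5) gives a unit for creatine kinase but none for SA.

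SAP 6.7.4 separately plans exploratory scatter plots and correlations of endpoint means, or least-squares means, against free SA.

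**The concern.** Serum SA is measured on a continuous scale, and the link between SA level and strength is part of the case for the higher dose. Protocol 7.4.3 lists, among the reasons for choosing 12 g/day, that SA level correlates with the treatment effect on HHD. An analysis of that link is more useful if it keeps the graded information in SA. A two-group split treats a subject just above the cut the same as one far above it.

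The split is also out of line with the rest of the SAP. Sections 6.8.1 to 6.8.8 use GEE to relate change in one measure to change in another (HHD lower extremity with 6MWT distance, for example) and describe no dichotomising.

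At stake is precision in a small sample: about 46 rollover subjects, or about 56 with the 10 treatment-naïve subjects. There is also a smaller practical risk. If 0.1 were applied to data held in micrograms/ml, the cut would sit at one tenth of the intended value.

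**Working it through.** The plan gives no power, sample size or efficiency figure for this analysis, so there is none to reproduce.

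**Inputs.** The cut of 0.1 mg/dl is from SAP 6.7.6 and the unit of micrograms/ml from SAP 6.9.1. The 46 rollover and 10 naïve subjects (46 + 10 = 56) are from SAP 6.1. The test level is from SAP 6.5: "All statistical tests will be two-sided and a difference resulting in a p-value of less than or equal to 0.05" counts as significant. The documents give no distribution or SD for SA change and no expected share of subjects above the cut, so these are assumed and varied below.

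**Units.** 0.1 mg/dl × 1000 micrograms/mg ÷ 100 ml/dl = 1.0 microgram/ml, an exact factor of 10.

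**Information kept.** If the relation is linear, the share of information kept by a split is the squared correlation between SA change and the indicator of being above the cut. For a normal predictor with share p on one side, this is φ(z_p)² / [p(1−p)]. At p = 0.5 it is 0.3989² / 0.25 = 0.637, which is 2/π.

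| Split | Kept | Lost | Equivalent of 46 | Equivalent of 56 |
|---|---|---|---|---|
| 50/50 | 0.637 | 36.3% | 29.3 | 35.7 |
| 70/30 | 0.576 | 42.4% | 26.5 | 32.2 |
| 80/20 | 0.490 | 51.0% | 22.5 | 27.4 |
| 90/10 | 0.342 | 65.8% | 15.7 | 19.2 |

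Under normality, 36.3% is the smallest possible loss, because any uneven split loses more.

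**Other distributions, relation still linear.**
- Uniform, share kept 3p(1−p): loss of 25% at 50/50, 28% at 60/40, 37% at 70/30 and 52% at 80/20.
- Two equal normal clusters split midway (simulated): loss of 32%, 25% and 19% with means at ±1, ±1.5 and ±2 SD.
- Right-skewed, lognormal with log-SD 0.5 (simulated): loss of 49% at the median, 39% with 80% of subjects below the cut, and 73% with 20% below.

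A loss of about a third is therefore not a general lower bound.

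**If the truth is a step at the cut.** The split is then the correct model. The squared correlation is symmetric, so for a normal predictor and a median cut it would be the straight-line term that kept only 63.7%.

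**Illustrative power.** This uses Fisher's z, one value per subject, an assumed true r = 0.4 and a normal predictor. Power = Φ(atanh(r)·√(N−3) − 1.96), with r multiplied by √(share kept) for a split.
- N = 46, continuous: 0.4236 × 6.557 − 1.96 = 0.818, giving 79%.
- N = 46, 50/50 split: r falls to 0.4 × √0.637 = 0.319, giving 58%. At 80/20, power is 47%.
- N = 56: 87% continuous, 67% at 50/50 and 55% at 80/20.

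These figures approximate the GEE, and r = 0.4 is not taken from the documents.

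**The case against.** The strongest reply is that the SAP does not ignore measured SA. The impact analysis and graphical trends in 6.7.6 and the correlations in 6.7.4 are commitments, whereas the split is something that may be done. GEE is the default for repeated-measures efficacy parameters under 6.7.2, so the impact analysis might be modelled that way. A reader might infer that the plan uses the split instead of the measured values. The documents do not support that. What stands is narrower: no method is given for the impact analysis, the correlations as worded are of endpoint means, and no subject-level adjusted model with continuous SA is written down. The table list in 8.1 has none for SA against HHD, although it is expressly not exhaustive.

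A second reply is that linearity is unproven. Protocol 7.4.3 reports an effect at 6 g and almost none at 3 g, which looks like a threshold, and Protocol 7.5.5 says free serum SA does not measure circulating drug quantitatively. Both cautions are fair. The first concerns dose and does not place a step at 0.1 mg/dl; the same section also reports a correlation of SA level with HHD effect. The second limits either form of the analysis.

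A third reply is that a continuous slope can be confounded. Naïve subjects start untreated, while rollovers have already taken SA-ER (Table 3) and have several candidate baselines (6.5.8). A pooled slope adjusted only for baseline HHD, age and gender would partly measure naïve versus rollover status. This stands in full and is met in the fix.

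**Conclusion.** The point holds as a modest improvement. The one SA-to-HHD model that the SAP specifies dichotomises a continuous exposure at an unexplained value, in a different unit from that of 6.9.1. If SA change is roughly normal and the relation linear, at least 36% of the information is lost, rising to 51% at 80/20 and 66% at 90/10. The documents establish neither assumption. Across the distributions tried, the loss ran from 19% to 78% (the latter a normal predictor split 95/5).

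Three stronger readings should be resisted.

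- A reader might infer that a third or more of the information is lost whatever the data look like. Near-even splits of uniform or clustered data lose less, and a true step at the cut does not lose it in this way.
- A reader might infer that the units are in error. Both sections print their unit and the conversion is exact, so this is a programming risk.
- A reader might infer that nearly everyone on 12 g/day will exceed the cut and leave the low group almost empty. Nothing in the documents gives the share above it.

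The consequence is small: the analysis is exploratory and optional, and SAP 6.1 says the study is not powered for comparisons.

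**What to change.** For the SA-impact analysis already promised in SAP 6.7.6, specify the same GEE with each subject's mean change in free serum SA as a continuous covariate. Adjust for baseline HHD, age, gender and prior-treatment pathway. Table 3 has five pathways, so full adjustment needs four indicator terms; a single naïve-versus-rollover term is the lighter alternative at this sample size. Name the SA baseline visit for each group. Report the slope per 1 microgram/ml with its 95% CI.

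Keep the two-group split as a descriptive display only, and state its cut as 1.0 microgram/ml.

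The cost is one model statement and a few lines of SAP text, with no new data. The downside is that the slope assumes approximate linearity. The scatter plots already planned can check this.

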6.7.7 Efficacy Analysis: Six-Minute Walk Test Distance

The Six Minute Walk Test (6MWT) will be used to evaluate change in walking capacity. 6MWT distance observed for the 12 g/day SA-ER/SA-IR treatment group will be summarized using descriptive statistics at each time point from Part II of UX001-CL202 (Table 2).

A GEE analysis model will be developed to examine the change in 6MWT distance for the 6-month part II analysis with study time points as categorical predictors and age, gender and Screening 6MWT distance as covariates. The defined baselines and planned comparisons to be examined in this analysis are identified in Table 8.

In addition the cross-over treatment pathway groups may be compared with the change observed in prior treatment period for the 6MWT. Trends in the change observed in 6MWT will be displayed using graphical techniques.

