6.7 Statistical Analysis: Clinical Efficacy

6.7.1 Planned Comparisons for Clinical Efficacy Parameters

The planned comparisons for UX001-CL202 are based on change from baseline assessments, where different baselines are utilized to evaluate treatment across a subject's treatment in

both UX001-CL201 and UX001-CL202. [Table 8](#) presents the planned comparisons for study data obtained in UX001-CL202 compared with study data from UX001-CL201 for roll-over subjects, as well as the treatment naïve subjects in UX001-CL202.

Clinical efficacy data collected in Part I of UX001-CL202 (all roll-over subjects dosed with 6g/day SA-ER) will not be included in planned comparisons for the clinical efficacy analysis.

Additional comparisons not specified in this statistical analysis plan may be completed as prospective analyses are completed to better understand study results. These additional comparisons will be clearly identified in final reporting.

Table 8 Planned Comparisons

Planned Comparison	Description
Primary Analysis #1: Week 24 12g/day SA/ER/SA-IR vs. Week 0	All subjects who roll-over from UX001CL201 will have their week 0 assigned as baseline (Part I termination visit of the 202 study) and the change from this score will be compared to the week 24 12g/day SA-ER/SA-IR treatment to assess the impact of the 12g/day SA-ER/SA-IR dose.
Primary Analysis #2: Week 24 12g/day SA/ER/SA-IR vs. Week 48 UX001-CL201 for 6/6+0/6 SA-ER	All subjects who roll-over from UX001CL201 will have their week 48 assigned as baseline and the change from this score will be compared to the week 24 12g/day SA-ER/SA-IR treatment to assess the impact of the 12g/day SA-ER/SA-IR dose across the combined 6/6+0/6 dose (UX001-CL201 subjects treated with 0/6 or 6/6 SA-ER will be combined for comparison from dosing pathways 1 and 3 from Table 3). A second comparison will be with a 6 minute walk test at Screening of ≥ 200 m (6MWT ≥ 200 m)
Primary Analysis #3: Week 24 12g/day SA/ER/SA-IR vs. Week 48 UX001-CL201 for 3/3+0/3	All subjects who roll-over from UX001CL201 will have their week 48 assigned as baseline and

Planned Comparison	Description

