In general, baseline value, gender, and age will be covariates in the GEE models for each planned analysis where appropriate. The final form of the GEE model for each clinical efficacy parameter and planned comparison will be described in the final study report.

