6.7.3 Statistical Modeling: Analysis of Covariance (ANCOVA)

Where appropriate, supportive analyses of clinical efficacy parameters may be completed with Analysis of Covariance (ANCOVA) (Kutner 2005). ANCOVA combines features of both analysis of variance (ANOVA) and regression. It augments the ANOVA model with one or more additional quantitative covariates, which are related to the response variable. The covariates are included to reduce the variance in the error terms and provide more precise measurement of the treatment effects. ANCOVA is used to test the main and interaction effects of the factors, while controlling for the effects of the covariate. In the analyses of this study, ANCOVA will be used for the variables that were measured at the baselines identified in [Figure 1](#). ANCOVA may be implemented to assess treatment group differences in comparisons identified in [Table 8](#) while controlling for the screening measure of the clinical efficacy variable being analyzed. ANCOVA may be utilized where repeated measures are not anticipated for a planned, supplemental analysis or in cases where further understanding of study results will benefit from the use of ANCOVA.

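### SAP 6.7.7 adjusts the 6MWT model for Screening distance, which conflicts with the baseline covariate in 6.7.2 and the baselines in Table 8, and matters where different subjects are contrasted

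*SAP*

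**What the plan says.** SAP 6.7.7 fits a GEE to change in 6MWT distance, with time points as categorical predictors and "age, gender and Screening 6MWT distance as covariates". It then refers elsewhere for the starting values: "The defined baselines and planned comparisons to be examined in this analysis are identified in Table 8". Section 6.7.8 uses a model of similar construction for percent predicted distance, so it inherits the covariate.

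Table 8 (SAP 6.7.1) sets these baselines:

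- **Primary #1:** the Part I Termination Visit.
- **Primary #2 and #3:** "All subjects who roll-over from UX001CL201 will have their week 48 assigned as baseline".
- **Roll-over Secondary Analysis:** UX001-CL201 Week 0.
- **Treatment-naive subjects:** their Week 0, which SAP 6.5.8 identifies as the Part II Screening/Baseline visit.
- **UX001-CL201 placebo comparators:** data from Week 0 to Week 24, so Week 0 is the starting value.

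The general model in SAP 6.7.2 has its own baseline term in the sample code. The text adds that "baseline value, gender, and age will be covariates in the GEE models for each planned analysis where appropriate". The supportive ANCOVA in 6.7.3 instead assesses group differences "while controlling for the screening measure of the clinical efficacy variable being analyzed".

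The parallel sections name the baseline where 6.7.7 names Screening: gait speed (6.7.9), weighted arm lift (6.7.11) and HIBM-FAS (6.7.12).

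**The concern.** Change from a starting value depends on that starting value, so the natural covariate is the value from which the change is measured. Section 6.7.7 names a different one and does not say which visit it is.

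- If Screening means the UX001-CL201 screening visit, it precedes the Week 48 baseline of Primary #2 and #3 by the length of that study.
- If it means the Part II Screening/Baseline visit (for roll-over subjects, the last Part I visit), it is the correct baseline for Primary #1 and for naive subjects. For #2 and #3 it falls after Week 48, inside the change interval. For placebo subjects it falls after their whole Week 0 to 24 period.

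A programmer could fit Screening only, baseline only, or both. Section 6.7.2 leaves the final model form to the study report, so the choice could be made with data in hand. The 6MWT belongs to the six-month analysis, which SAP 6.3 calls primary for clinical efficacy. At stake are precision, and bias in any contrast between subjects whose starting distances differ.

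**Working it through.** **Inputs from the documents.** Exchangeable correlation (SAP 6.7.2), about 46 roll-over subjects (SAP 6.1), and the covariates and baselines above. The documents give no SD or visit-to-visit correlation for the 6MWT and no power calculation, so there is no stated figure to reproduce.

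**Assumptions.** Equal variance σ² at screening (S), the change baseline (B) and follow-up (Y). Correlations are r for B and Y, q for S and B, and p for S and Y, with r between 0.7 and 0.9. Any baseline imbalance between groups is chance imbalance between samples of one population. The simulations (6,000 runs) add a mean of 300 m, SD 100 or 150 m, N = 46 (split 23/23 for two groups) and no true effect.

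**Step 1: one group, change from its own baseline.** With a centred covariate, the fitted mean change is the sample mean of Y − B, whatever the covariate. At r = 0.8 and SD 100 m, the simulated mean change is −0.25 m with standard error 9.34 m, identical with no covariate, with S and with B. The algebra agrees: 100 × √(2 × 0.2 / 46) = 9.3 m.

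**Step 2: residual variance of the change.**

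- Adjusted for B: σ²(1 − r²).
- Adjusted for S: σ²[2(1 − r) − (p − q)²].
- Under exchangeable correlation p = q = r, so the last term is zero and the ratio is 2(1 − r)/(1 − r²) = 2/(1 + r).

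**Step 3: bias from a chance difference of d metres in B.**

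- Adjusted for B: none.
- Adjusted for S: −[(1 − r) + (p − q)q] × d.
- Under exchangeable correlation this is −(1 − r) × d. The slope of change on S is zero, so S corrects nothing.

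| r | Variance ratio 2/(1 + r) | Standard error ratio | Bias per metre, S | Bias per metre, B |
|---|---|---|---|---|
| 0.9 | 1.05 | 1.03 | −0.10 | 0 |
| 0.8 | 1.11 | 1.05 | −0.20 | 0 |
| 0.7 | 1.18 | 1.08 | −0.30 | 0 |

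Simulation check at r = 0.8 and SD 100 m: the two-group estimate has SD 19.1 m with S and 18.1 m with B, and (19.1/18.1)² = 1.11. Simulated bias per metre with S is about −0.20 at r = 0.8 and −0.10 at r = 0.9; with B it is about 0.

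**Step 4: correlation that decays over time.** Here p = qr, and the bias becomes −(1 − r)(1 − q²) × d. The simulated slope of change on S is −0.148 at r = 0.8 and −0.087 at r = 0.9. This slope equals −q(1 − r), so q = 0.148/0.20 = 0.74 and 0.087/0.10 = 0.87.

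- r = 0.8: bias per metre −0.20 × (1 − 0.74²) = −0.09; variance ratio (0.40 − 0.148²)/0.36 = 1.05.
- r = 0.9: bias per metre −0.10 × (1 − 0.87²) = −0.02; variance ratio (0.20 − 0.087²)/0.19 = 1.01.

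**Example.** A 20 m imbalance at r = 0.9 leaves 0.10 × 20 = 2 m under exchangeable correlation and about 0.02 × 20 = 0.4 m under decay.

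**Step 5: where this applies.** The Treatment Naive Secondary Analysis contrasts naive subjects with UX001-CL201 placebo subjects. For naive subjects, screening and baseline are one visit (Protocol 7.5.1), so the covariate is already the change baseline. For placebo subjects it is not, if UX001-CL201 screening was separate from Week 0. The documents do not say whether it was. With only one arm mismatched, the table is a guide to size, not an exact figure. The ANCOVA in 6.7.3 is the other place where group differences are planned.

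**The case against.** **The SAP does not say that Screening replaces the baseline.** Section 6.7.2 governs all repeated-measures efficacy endpoints and carries a baseline term; nothing gives 6.7.7 precedence, and 6.7.7 itself points to Table 8. This stands. A reader might infer that the 6MWT model drops the baseline, but the text supports only a contradiction and an undefined visit label. The contradiction still needs resolving, because both readings can be programmed.

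**Primary #2 and #3 are changes from the subjects' own Week 48 value.** This also stands. A reader might infer that regression to the mean is left uncorrected in these two analyses. Step 1 shows that the covariate does not move a single group's mean change, so the named covariate neither creates nor cures such a bias. The 200 m subgroup is selected on Screening, not on Week 48. Its spurious change from Week 48 is about 0 m under exchangeable correlation and −1.3 to −9.2 m under the simulated decay (correlations 0.80 to 0.95). The covariate would matter in #2 and #3 only if the treatment indicators in 6.7.2 were used to contrast different subjects.

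**The metre values rest on assumptions.** They do. For example, a bias of 5 to 15 m needs a 50 m imbalance, which appears nowhere in the documents, and no help from the screening value.

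**Consequences are limited.** The study is open-label and not powered for comparisons, and the ANCOVA is optional. That bears on priority, not on whether to correct the wording.

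**Conclusion.** The point holds as an internal conflict with a limited statistical cost. Sections 6.7.7 and 6.7.3 name a screening value, 6.7.2 names the baseline, and Table 8 sets Week 48 for Primary #2 and #3, which Screening is not on either reading. The single-group mean changes are unaffected. In contrasts between different subjects, the cost under exchangeable correlation and r of 0.7 to 0.9 is about 5 to 18% more residual variance (standard errors about 3 to 8% larger) and 0.1 to 0.3 m of bias per metre of chance baseline imbalance. Both are smaller under decaying correlation. The correlations are assumed, and in the naive-versus-placebo contrast the cost also depends on UX001-CL201 screening having been a visit separate from Week 0. This is a minor point, worth correcting because the better covariate is already collected.

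**What to change.** In SAP 6.7.7 (and so in 6.7.8) and 6.7.3, replace the screening value with the baseline value defined in Table 8 for that comparison:

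- Part I Termination Visit for Primary #1.
- UX001-CL201 Week 48 for Primary #2 and #3.
- UX001-CL201 Week 0 for the roll-over Secondary Analysis and for placebo subjects.
- Part II Screening/Baseline for treatment-naive subjects.

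Separately, state which visit Screening means where it defines the 200 m subgroup in Table 8. The cost is one phrase in two sections and one definition. No new data are needed, and the 6MWT then follows the same pattern as the parallel endpoints.
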